10.0 EVALUATION DURING TREATMENT/INTERVENTION

- 10.1 Prior to each cycle of chemotherapy, the patient will have an interval history, toxicity evaluation and physical examination, including vital signs, and performance status.
- 10.2 CBC with differential, and comprehensive profile will be required prior to each cycle of chemotherapy.
- 10.3 After completion of 2 cycles of clofarabine, the patient will be assessed or reassessed for response as per section 9.6.
- 10.4 If the patient has achieved a complete response (CR), a repeat bone marrow biopsy will be performed only in those cases where it had been previously positive.
- 10.5 Following completion of the treatment plan, responding patients should be followed at three month intervals for the first two years post-therapy to document duration of response.

**Sponsor: Memorial Sloan-Kettering Cancer Center
IRB Protocol**

IRB#: 06-065A(4)

Table 10.0 Study Calendar

Assessments	Pre-treatment		Day 1 Cycle 1	Day 8 Cycle 1	Day 15 Cycle 1	Day 22, 29, 36 Cycle 1 ^a	Day 1 Cycle 2	Day 8 Cycle 2	Day 15 Cycle 2	Day 22, 29, 36 Cycle 2 ^a	Off study/ Cont Rx
	≤ 30 days prior to Rx	≤ 14 days prior to Rx									
Clofarabine			XXX				XXX				
Informed consent and/or assent		X									
Medical history and height (cm)		X									
Interval history, incl. AE eval. and med list		X	X			X	X			X	X
PE, VS, incl. wt and ECOG PS		X	X			X	X			X	X
Cbc with differential		X	X	X	X	X	X		X	X	X
Serum chemistry ^b		X	X	X	X	X	X		X	X	X
LDH		X									X
Coagulation profile / urinalysis		X									
Beta-HCG ^c		X									
Viral serologies ^d	X										
EKG	X										X
Echo or MUGA	X										X ^e
Chest Xray	X										
Tumor imaging ^f	X										X
Bone marrow biopsy	X										X ^g

^aIf the re-treatment criteria is not met at the day 22 ± 2 day evaluation, the treatment will be withheld and the patient will be re-evaluated the following week(s), up day 36 ± 2 days from the beginning of therapy.

^bSerum chemistry: albumin, alkaline phosphatase, total bilirubin, bicarbonate, BUN, calcium, chloride, creatinine, glucose, phosphorus, potassium, total protein, SGOT (AST), SGPT (ALT), sodium, magnesium, uric acid

^cSerum or urine beta-HCG is required for all women of childbearing potential.

^dViral serologies: HIV, Hep B S Ag, Hep B S Ab, Hep C Ab, HTLV-1

^eEchocardiogram/MUGA: A followup echocardiogram or MUGA must be ordered if the dose level is at or above 28 mg/m²/d

^fTumor imaging: CT of the chest, abdomen and pelvis, and CT or MRI of extranodal sites (if indicated). Followup PET scan is encouraged (not required) only if baseline PET scan was positive

^gFollowup bone marrow biopsy is required only if: 1) previously positive and 2) disease is in complete remission per define criteria.

**Sponsor: Memorial Sloan-Kettering Cancer Center
IRB Protocol**

IRB#: 06-065A(4)

11.1 TOXICITIES/SIDE EFFECTS

As stated in section 5.0, the dose-limiting toxicity for patients with solid tumors or lymphoid malignancies was myelosuppression. For the patients with acute leukemia who were treated with much higher doses of clofarabine (40-52 mg/m²/d), the dose-limiting toxicity was hepatotoxicity and rash. More specifically, potential toxicities include hyperbilirubinemia, transaminitis, neutropenia, leukopenia, thrombocytopenia, anemia, nausea, and vomiting. Other side effects which have been seen rarely in early trials include rash, myalgia, fatigue, diarrhea, constipation, mucositis, urinary incontinence, headache, fever, chills, anorexia, palmar-plantar erythrodysesthesia, anxiety, bone pain, cough, tachycardia, congestive heart failure, abdominal pain, seizure, hypertension, respiratory distress, and capillary leak syndrome.

An objective of this study is to obtain information on the safety and efficacy of clofarabine for patients with previously treated mature T-and NK-cell lymphoma. It is the Investigator's obligation to report all adverse experiences (AE's), regardless of association with study drugs.

11.2 Definitions of AE's

11.2.1 Adverse Experience: An AE is defined as any untoward medical occurrence in a patient administered a pharmaceutical product which does not necessarily have a causal relationship or association with the treatment. Laboratory abnormalities should only be recorded as AE's if they are associated with clinical sequelae and/or require an intervention.

11.2.2 Serious Adverse Experience (SAE): An SAE is considered to be any experience occurring at any dose that results in any of the following outcomes: (1) is fatal or life-threatening ("Life-threatening" means that the event, as it actually happened, placed the subject at immediate risk of death.), (2) is disabling, (3) results in hospitalization or prolongation of hospitalization, or (4) results in congenital anomaly or occurrence of malignancy. Important medical events that may not result in death may be considered SAE's when, based upon appropriate medical judgment, they may jeopardize the patient and may require medical or surgical intervention to prevent one of the outcomes listed in this definition.

11.2.3 Expected Adverse Experience: Any AE that is identified in the current Investigator's Brochure or in Section 5 and/or Section 11 is considered an expected AE.

11.2.4 Unexpected Adverse Experience: An AE which is not previously reported (in nature, severity, or incidence) in the current Investigator's Brochure or general investigational plan.

**Sponsor: Memorial Sloan-Kettering Cancer Center
IRB Protocol**

IRB#: 06-065A(4)

11.3 Serious Adverse Experience Reporting Requirements

For Participating Sites:

Any SAE will be reported to the local institution's IRB. In addition, it will need to be sent to MSKCC as the coordinating center and Genzyme as soon as possible but no later than 5 days from the onset of the event.

The Study PI will fax a copy of all SAE's within 5 days to outside site principal investigators to report to their own local IRB's.

Participating sites should send the following information to the coordinating center:

1. The initials of the subjects, patient MRN #, MSKCC protocol # and title
2. The date the event occurred
3. A description of the SAE
4. An explanation of how the SAE was handled
5. A description of the subject's condition
6. Indication if the subject remains on the study
7. Indication if the event is considered related to the treatment (drug, device, intervention)
8. Indication if an amendment will need to be made to the protocol and/or consent form as a result of the SAE.
9. Name of the site and person reporting the event

Refer to section 17.2.

11.4 SAE Followup

For all SAEs occurring during the study, within 30 days of the last administration of study drug, or prior to alternative therapy (whichever occurs first), the investigator must submit follow-up reports to Genzyme regarding the patient's subsequent course until the SAE has subsided, or until the condition stabilizes (in the case of persistent impairment), the patient receives alternative treatment, or the patient dies.

12.0 CRITERIA FOR THERAPEUTIC RESPONSE/OUTCOME ASSESSMENT

Response and progression of disease will be evaluated in this study using a modification of the international criteria proposed by the Cheson et al. [29].

**IRB
PB**

Amended: 8/26/08

**Sponsor: Memorial Sloan-Kettering Cancer Center
IRB Protocol**

IRB#: 06-065A(4)

- 12.1.1 Measurable disease: Measurable lesions are defined as those that can be accurately measured in at least one dimension (longest diameter to be recorded) as ≥ 15 mm with conventional techniques (PET, CT, MRI, x-ray). All tumor measurements must be recorded in millimeters (or decimal fractions of centimeters).
- 12.1.2 Non-measurable disease: All other lesions (or sites of disease), including small lesions (longest diameter < 15 mm with conventional), are considered non-measurable disease. Bone lesions, leptomeningeal disease, ascites, pleural/pericardial effusions, lymphoma cutis/pulmonis, inflammatory breast disease, abdominal masses (not followed by CT or MRI), and cystic lesions are all non-measurable.

12.2 Response Criteria

Response criteria will be based on assessment following every 2 cycles of clofarabine. The criteria are as follows (GTD = Greatest Transverse Diameter; SPD = Sum of the Products of the Greatest Diameter):

12.2.1 Complete Remission (CR):

- No clinical, radiographic or diagnostic evidence of disease.
- No disease related symptoms.
- Abnormal biochemical values (eg. LDH) clearly attributable to lymphoma must have normalized.
- Lymph nodes, nodal masses regressed to “normal” size:
- If > 1.5 cm before treatment, regressed to ≤ 1.5 cm in GTD.
- If 1.1 to 1.5 cm before treatment, regressed to ≤ 1 cm in GTD (or $> 75\%$ in SPD).
- Spleen and all previously enlarged organs decreased in size. Spleen must not be palpable on exam
- Bone marrow free of disease on repeat aspirate and biopsy if initially positive.
- Normalization of PET scans.

12.2.2 Complete Remission/unconfirmed (CRU):

Patients meeting the above criteria for CR with the following exceptions:

- Residual node mass of > 1.5 cm in GTD regressed by $> 75\%$ in SPD
- Individual nodes previously confluent regressed by $> 75\%$ in SPD
- Indeterminate bone marrow (increased number or size of lymphoid aggregates without cytologic or architectural atypia.)

12.2.3 Partial Remission (PR)

- $\geq 50\%$ decrease in SPD of the six largest dominant nodes/nodal masses.
- No increase in size of other nodes, liver or spleen.

IRB
PB

Amended: 8/26/08

**Sponsor: Memorial Sloan-Kettering Cancer Center
IRB Protocol**

IRB#: 06-065A(4)

- Splenic and hepatic nodes regressed at least 50% in SPD
- No new sites of disease.
- Bone marrow and organs other than the spleen and liver cannot be considered for evaluation for PR because involvement at these sites is considered evaluable but not measurable.

12.2.4 PET negative Partial Remission (PET- PR)

- Patient meets above criteria for PR with resolution of previous PET positive lesions.

12.2.4 Stable Disease (SD)

- Patients who have achieved less than a partial remission but who have not developed findings consistent with progressive disease.

12.2.5 Progressive Disease (PD)

- In patients previously CR, Cru, PR or SD.
- $\geq 50\%$ increase in SPD of any previously identified abnormal node.
- Appearance of any new lesion during or at the end of therapy

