- For the phase II portion of the trial, patients must have measurable disease defined as any nodal site or mass lesion ≥ 1.5 cm in longest transverse diameter on physical exam or computed tomography scan or a measurable extranodal site > 1 cm.
- For patients with primarily blood or marrow based disease, evaluable patients will be eligible
- Signed informed consent and/or assent.

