9.7 Treatment beyond 2 cycles

9.7.1 Following 2 cycles of clofarabine

Patients with stable disease, a partial response, or a complete response will receive 2 more cycles of clofarabine.

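### Growth of known disease outside the nodes is not progression under 12.2.5 and, unless it is in liver or spleen, does not block a partial remission under 12.2.3

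*Combined protocol and SAP*

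**What the plan says.** Section 12.2 gives a closed list of response criteria, applied after every two cycles.

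- **Progressive disease (12.2.5)** has two triggers: a ≥50% "increase in SPD of any previously identified abnormal node", or "Appearance of any new lesion during or at the end of therapy".
- **Partial remission (12.2.3)** needs a ≥50% "decrease in SPD of the six largest dominant nodes/nodal masses", no new sites, and "No increase in size of other nodes, liver or spleen". Its last bullet adds: "Bone marrow and organs other than the spleen and liver cannot be considered for evaluation for PR".
- **Stable disease (12.2.4)** is what remains: "Patients who have achieved less than a partial remission but who have not developed findings consistent with progressive disease".
- **Complete remission (12.2.1)** requires no evidence of disease at any site.

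Phase II (6.2) admits patients whose measurable disease is an extranodal site, and adds: "For patients with primarily blood or marrow based disease, evaluable patients will be eligible".

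Two parts of the plan act on these classes. Section 14.6 counts PR and CR: at least 1 response in 8 to continue, and at least 4 in 18 to call the drug worthy of further study. Section 9.7.1 says: "Patients with stable disease, a partial response, or a complete response will receive 2 more cycles of clofarabine". Section 9.7.3 makes progression at any time a treatment failure with removal from study.

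**The concern.** The growth trigger for progression names nodes only. The PR no-growth condition names nodes, liver and spleen only. Growth of a known lesion in skin, bowel, nasal passages or lung, or of known blood disease, falls under neither. Growth of known liver or spleen disease blocks PR but is not a progression trigger.

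Three things are at stake. A mixed response, with nodes shrinking while another known site grows, can enter the primary phase II endpoint as a PR. A patient whose only disease is extranodal or in the blood is recorded as stable when that disease grows, which sits badly with 9.7.3. Response duration, which section 2.1 says will be collected, would run too long if growth at a known site did not end it.

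**Working it through.** **Step 1. Apply the criteria to cases.** The sizes are illustrative.

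| Case | PR (12.2.3) | PD (12.2.5) | Recorded as |
|---|---|---|---|
| Nodes fall from 12 to 5 cm² (7/12 = 58% decrease); a known skin lesion grows from 2 to 5 cm; nothing new | All conditions met | Neither trigger met | PR |
| Same nodes; known liver or spleen disease enlarges | Blocked | Neither trigger met | SD |
| No nodal disease; a known extranodal lesion or blood disease grows | No nodes to shrink | Neither trigger met | SD |
| Any patient with a new lesion | Blocked | Met | PD |

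A false PR therefore needs both shrinking nodes and a growing known site outside nodes, liver and spleen. A patient with no nodal disease can be a false SD but not a false PR.

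**Step 2. Reproduce the plan's design (14.6).** Inputs: uninteresting rate 0.10, promising rate 0.35, both error limits 0.10, 8 patients then 10 more, continue on ≥1 response, succeed on ≥4 of 18.

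- Early stopping at 0.10: 0.9⁸ = 0.430. The plan states 43%.
- Probability of a positive trial: Σ over x = 1 to 8 of P(X₁ = x) × P(X₂ ≥ 4 − x), with X₁ ~ Bin(8, p) and X₂ ~ Bin(10, p).
- At p = 0.10:
  - x = 1: 0.3826 × 0.0702 = 0.0269
  - x = 2: 0.1488 × 0.2639 = 0.0393
  - x = 3: 0.0331 × 0.6513 = 0.0215
  - x ≥ 4: 0.0050
  - total: 0.093
- At p = 0.35 the same sum gives 0.906. The plan states at least 90%.

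The design is correctly calculated. Its type I error has 0.100 − 0.093 = 0.007 to spare.

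**Step 3. Add miscounted PRs.** Let f be the share of true non-responders recorded as PR through this gap. The documents give no value, so f is an assumption. With a true rate of 0.10, the counted rate is 0.10 + 0.90f.

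| f (assumed) | Counted rate | Stops at stage 1 | False-positive trial |
|---|---|---|---|
| 0 | 0.100 | 0.430 | 0.093 |
| 1% | 0.109 | 0.397 | 0.118 |
| 2% | 0.118 | 0.366 | 0.147 |
| 3% | 0.127 | 0.337 | 0.178 |
| 5% | 0.145 | 0.286 | 0.246 |

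The 0.10 limit is crossed at a counted rate of about 0.103, which is f of about 0.3%.

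**Step 4. The opposite direction.** PR requires nodal shrinkage, so a patient with only extranodal disease that shrinks but does not clear cannot score PR. If an assumed 10%, 20% or 30% of true responders were lost this way, the counted rate under 0.35 would be 0.315, 0.280 or 0.245, and power would fall from 0.906 to 0.85, 0.76 or 0.65.

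**The case against.** **Other text might close the gap.** Section 12.0 calls the criteria a modification of published international criteria, but does not say that the publication governs where the list is silent. The SD wording speaks of findings consistent with progression, which is looser than meeting 12.2.5 and leaves an assessor some room. That room lies only between SD and PD. It does not undo a PR whose conditions are all met.

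**Patients need not stay on treatment.** This stands. Section 4.4 allows treatment to continue only while removal criteria are unmet, and 13.0 lists both progression and investigator decision. A reader might infer from 9.7.1 that the plan obliges further cycles in someone who is evidently progressing; read with 4.4 and 13.0, it does not. But neither section defines progression or changes the recorded response, so the inconsistency with 9.7.3 remains. SD does not enter the response counts.

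**False PRs may be rare.** This also stands. A reader might note that the classification table in section 3 places only 3 of the 13 eligible subtypes under the predominantly nodal heading, and infer that false PRs will be common. The table does not support that. Only 5 of the other 10 are labelled predominantly extranodal; the remaining 5 are grouped as precursor or leukaemic, which is not a statement of disease site. Subtypes are not patients, and no enrolment mix is given. Patients without nodal disease cannot be false PRs at all; for them the wording points towards missed responses.

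**Conclusion.** The gap in the definitions is certain from the text. Its frequency is unknown, and so is its net effect on the response rate. Under an assumed 1% to 5% of true non-responders miscounted as PR, the false-positive probability is 0.118 to 0.246 instead of 0.093. The loss of extranodal-only responders pulls the other way.

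A reader might take counted rates of 15% or 20% as the likely result, with false-positive probabilities of 0.27 and 0.48. Starting from 10%, those rates need 0.05/0.90 = 5.6% or 0.10/0.90 = 11.1% of non-responders to be false PRs, so that one in three or one in two counted responders would be false. Nothing in the documents supports that. Nor can known disease grow unchecked in every class: a new lesion is always progression, liver or spleen growth blocks PR, and CR is protected.

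This should be fixed. It is a repairable weakness in the primary endpoint's definition and does not call the sample-size calculation into question.

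**What to change.** 1. **12.2.3:** extend the no-growth condition to every known disease site assessed at restaging. State that the last bullet stops marrow and other organs from establishing a PR, not from ruling one out.
2. **12.2.5:** extend the growth trigger to any previously identified measurable lesion, including liver, spleen and extranodal sites. Add unequivocal progression of known non-measurable disease, including skin, lung and blood. The second part is needed because 12.1.2 classes skin and lung lymphoma as non-measurable.
3. **Marrow:** count it only where it has been assessed. Follow-up marrow is scheduled only for patients with a positive baseline who are otherwise in CR, so a general marrow-rise rule would need new biopsies. None are proposed, and progression confined to marrow may still go unseen.
4. **9.7.1 and 9.7.3:** reconcile both with the revised definition of progression.

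**Cost.** A protocol amendment and matching response-form instructions. CT or MRI of relevant extranodal sites is already part of restaging, and examination and CBC with differential already precede each cycle. A few patients now called PR or SD will become SD or PD, so the reported response rate may be slightly lower. With this gap closed, f from this source is zero and the design keeps its figures of 0.430, 0.093 and 0.906. The change does not recover extranodal-only partial responses, so the report should state that limit.

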2.1 OBJECTIVES AND SCIENTIFIC AIMS

- To determine the maximum tolerated dose of intravenous clofarabine using the schedule outlined below that can be administered safely to patients with relapsed and refractory T- and NK-cell lymphomas.
- To define the toxicity of clofarabine using the proposed schedule in patients with relapsed and refractory T- and NK-cell lymphomas.
- To make a preliminary assessment of efficacy of intravenous clofarabine at the maximum tolerated dose in patients with relapsed and refractory T- and NK-cell lymphomas.
 - The primary statistical endpoint to evaluate efficacy in the phase II portion will be response rate. Data will also be collected on response duration.

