9.7.3 Progression of disease

Patients with progression of disease at any time will be declared treatment failures and removed from the study.

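### New lesions stop counting as progression when therapy ends, although responders are followed for two more years to measure response duration

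*Combined protocol and SAP*

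**What the plan says.** Section 2.1 makes response rate the phase II efficacy endpoint and adds: "Data will also be collected on response duration". Item 10.5 in section 10.0 provides the follow-up for this: "responding patients should be followed at three month intervals for the first two years post-therapy to document duration of response".

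Section 12.2.5 defines progressive disease in three bullets:
- the patients concerned: "In patients previously CR, Cru, PR or SD";
- a rise of at least 50%, worded as an "increase in SPD of any previously identified abnormal node", with no reference value and no time limit;
- new lesions: "Appearance of any new lesion during or at the end of therapy".

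Three other places bear on the reading. Section 12.0 says: "Response and progression of disease will be evaluated in this study using a modification of the international criteria". Section 12.2 says: "Response criteria will be based on assessment following every 2 cycles of clofarabine". Section 9.7.3 says: "Patients with progression of disease at any time will be declared treatment failures and removed from the study".

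The protocol does not define relapse separately. It gives no start, end event, censoring rule or analysis method for response duration. Section 14.7 only tabulates response and toxicity.

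**The concern.** The follow-up in item 10.5 exists to date the end of a response. The only rule that could date it stops counting new lesions once treatment is over. A patient in complete remission who relapses six months after the last cycle, at a new site only, has no new lesion in the permitted window and no growing old node. As written, that patient has not progressed.

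The node criterion has a different weakness. Because the reference value is missing, two assessors can give the same patient different progression dates.

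At stake is response duration, the one efficacy outcome besides response rate for which section 2.1 plans data. Few patients will contribute to it. Section 14.6 allows at most 18 phase II patients and calls the drug worth pursuing at 4 responses, so one or two misdated relapses could move a median.

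**Working it through.** **1. The plan's own figures.** Section 14.6 gives a Simon minimax design: 8 patients, stop at 0 responses; otherwise 18 patients, success at 4 or more. The null and target rates are 10% and 35%.
- Early stopping at 10%: 0.9^8 = 0.4305 (the plan says 43%).
- Probability of success at rate p: the sum over x = 1 to 8 of P(X1 = x) × P(X2 ≥ 4 − x), with X1 ~ Bin(8, p) and X2 ~ Bin(10, p). This gives 0.0927 at 10% and 0.9062 at 35%. Both meet the stated 0.10 error limits.

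None of these figures uses the date on which a response ends. The plan gives no figure for duration.

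**2. Which post-therapy relapses meet section 12.2.5, read literally?**

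| Relapse after therapy in a responder | Meets the definition? |
|---|---|
| Regrowth of at least 50% in a previously abnormal node | Yes, at any time (reference value unclear) |
| New lesion only | No, outside the stated window |
| Blood or marrow only | Not named in either criterion |

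The last row matters because section 6.2 admits patients with mainly blood or marrow disease.

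**3. How much of a response falls after therapy?** Sections 4.4 and 9.7.2 allow at most 2 cycles beyond maximum response. Section 9.5 implies 21 to 35 days per cycle, ignoring the ±2-day windows. That is 42 to 70 days. For a response lasting 182 days beyond its maximum, the share after therapy is (182 − 70)/182 = 62% to (182 − 42)/182 = 77%.

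**4. Node reference value** (illustrative SPD, baseline 100). The threshold is 1.5 × the reference, so the two readings differ by the ratio of baseline to smallest value.

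| Smallest SPD | Threshold from smallest | Threshold from baseline | Ratio |
|---|---|---|---|
| 50 | 75 | 150 | 2 |
| 40 | 60 | 150 | 2.5 |
| 25 | 37.5 | 150 | 4 |
| 10 | 15 | 150 | 10 |

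These are tumour burdens, not times.

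**5. Possible effect on a median duration (assumption only).** Suppose the time to relapse is exponential with true median m, and a share f of relapses is new-lesion-only and uncounted. Suppose also that those patients either leave the risk set at that point or keep the same hazard of a countable event. The apparent hazard is then (1 − f) times the true one, and the apparent median is m/(1 − f).

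| True median (months) | f = 0 | f = 0.25 | f = 0.5 | f = 0.75 |
|---|---|---|---|---|
| 6 | 6 | 8 | 12 | 24 |
| 12 | 12 | 16 | 24 | 48 |

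The documents do not give f. The table treats every relapse as post-therapy, which overstates the effect, since new lesions on treatment are counted.

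**The case against.** The strongest reply is that the protocol does register most relapses.

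- The node criterion has no time limit and names patients already in response, so nodal regrowth during follow-up is progression. This stands. A reader might infer that no relapse in the two-year follow-up ends a response; the text does not support that.
- Section 9.7.3 speaks of progression at any time. But it uses a term that only section 12.2.5 defines, so it does not widen the window.
- Complete remission (12.2.1) requires no evidence of disease, and partial remission (12.2.3) requires no new sites. A sensible investigator could therefore end the response when a new lesion appears. This is fair, and it makes overstatement a risk rather than a demonstrated result. Still, nothing in the protocol makes loss of remission status the end event.
- The criteria modify a published standard that may cover relapse. The protocol does not say that unlisted parts of that standard apply.
- The missing reference value is an ambiguity, not a bias in itself. That is right: only the baseline reading delays progression.

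A reader might also infer that a patient who progresses at the first restaging falls outside the definition, because of the bullet listing prior categories. The stable-disease definition in 12.2.4 excludes patients with findings of progression, and 9.7.3 covers any time. Such a patient has no response whose duration could be affected.

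**Conclusion.** The conflict between section 12.2.5 and item 10.5 is real but narrow. On a literal reading, a responder whose post-therapy relapse appears only as a new lesion never meets progression, and the recorded duration is too long. Separately, the node criterion leaves the progression date ambiguous, with thresholds of 60 or 150 in the 100-to-40 illustration.

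The size of any bias is unknown. It depends on the share of new-lesion-only relapses, which the documents do not give, and on how literally assessors apply the rule. The apparent medians above show a range under assumptions and are not estimates for this trial.

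Response duration is a secondary, descriptive outcome. The response rate, the 8- and 18-patient stages and their error rates do not change.

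A reader might conclude that durations here could not be compared with the 6 to 15 months quoted in section 3.4. That depends on how the cited studies defined duration, which the documents do not show. The remark there about responses not lasting concerns deoxycoformycin alone, not existing drugs in general.

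**What to change.** For outcome assessment:

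1. In section 12.2.5, count new lesions at any time during therapy or follow-up.
2. State that the rise of at least 50% in SPD is measured from the smallest recorded value.
3. Define response duration as the time from first documented CR, CRu or PR to progression, relapse or death. Relapse should include blood or marrow relapse for patients with that disease. Patients without an event are censored at their last disease assessment.

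Section 9.7.3 uses the same term for removal from study, so the sponsor should say whether the revised definition is for outcome assessment only.

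The cost is protocol wording; the three-monthly visits are already planned. Item 10.5 does not say what disease assessment those visits include. That should be stated, because the censoring date depends on it; any added imaging would cost more than wording. The downside is that reported durations may be shorter.
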